## 4.2 Screen Failures

Screen failures are defined as individuals who consent to participate in the clinical study but who do not meet the eligibility criteria for participation (see [Section 4.1](#)) by Baseline.

A minimal set of information including demography, eligibility criteria, screen failure details, and any SAE should be recorded for all individuals considered screen failures.

Individuals who do not meet the eligibility criteria by Baseline (ie, screen failure) other than actual DM diagnosis and disease activity may be rescreened once for failed eligibility.

## 4.3 Discontinuation of IMP and Subject Study Withdrawal

### 4.3.1 Discontinuation of IMP

If any of the following apply, the subject must discontinue IMP:

- Subject wishes to discontinue IMP
- Subject withdraws consent for study participation
- Investigator advises that the subject's safety or well-being could be compromised by further treatment
- Subject or caregiver is not able to administer the SC infusions at home by Week 4
- Subject has confirmed diagnosis of DVT or PE
- Subject has Grade 3 hemolysis (see [Section 8.1.2.3](#))
- Subject becomes pregnant
- Relevant treatment noncompliance

During participation in Study Period 3, if the investigator determines that the subject is no longer benefiting from IgPro20 and/or is showing signs of clinical deterioration in DM status, the subject must be discontinued from the study.

The investigator should record in the electronic case report form (eCRF) and in the subject's medical records the reason and date of IMP discontinuation.

Subjects who discontinue IMP will be encouraged to remain in the study until Week 25 if discontinuation occurs during Study Period 1, or until Week 53 if discontinuation occurs during Study Period 2, in order to collect study assessments. The Safety Follow-up Telephone Call will not be performed for subjects who discontinue IMP treatment but remain in the study for at least 1 subsequent study visit 4 weeks after IMP discontinuation. See [Schedule of Assessments](#) for details on assessments no longer collected after IMP discontinuation if the subject remains in the study, and Section 4.3.2 for details on handling subject withdrawal from study.

Subjects who discontinue IMP during Study Period 3 will be withdrawn from the study. Withdrawal from IMP Study Period 1 or Study Period 2 renders a subject ineligible for participation in Study Period 3 of this study.

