**Notes for the Schedule of Assessments for Study Period 3:**

- For subjects who discontinue IMP during participation in Study Period 3, all EOP3 assessments will be performed at the study visit where subjects discontinue/end study participation.
- A urine pregnancy test will be performed on all female subjects of childbearing potential.
- Vital sign assessments include supine systolic and diastolic blood pressure, pulse rate, respiratory rate, and body temperature.

- D. Hematology: hemoglobin, hematocrit, platelets, erythrocytes, leukocytes with differential counts (neutrophils, basophils, eosinophils, lymphocytes, monocytes).
- E. Biochemistry: sodium, potassium, chloride, bicarbonate, BUN, glucose, GGT, alkaline phosphatase, creatinine.
- F. Four individual CSMs will be assessed in Study Period 3: Physician Global Disease Activity and Patient Global Activity Assessment, MMT-8, and HAQ.
- G. Additional IMP will be assigned at UNS Visit if the subject's weight has increased ( $> 2$  kg), which will require a dose volume increase (see [Appendix 15](#)).
- H. IMP will be dispensed at this visit only if the subject is continuing in Study Period 3.

**Table 4** Schedule of Assessments for Rich Pharmacokinetic Sampling

Study Week	Week 37				
	Sampling Time A	+24 ± 3 h relative to the start of first infusion	+48 ± 3 h relative to the start of first infusion	+72 ± 3 h relative to the start of first infusion	+120 ± 3 h relative to the start of first infusion
Serum for IgG levels B	X	X	X	X	X
Serum for exploratory biomarkers	X	X	X	X	X

h = hours; IgG = immunoglobulin G.

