studies have been conducted and are summarized in a systematic review [Wang et al, 2012]. Clinical improvement was reported in up to 93% of subjects in early and therapy-refractory DM/PM; the typical dose was 2 g/kg IVIG given over 3 to 6 months. It has been reported that long-term use of IgG therapy is safe and effective, but this has not yet been confirmed in clinical studies. In a retrospective long-term study, 42 subjects with DM were followed; 24 received IVIG therapy regularly. After 6 months of treatment, most IVIG-treated subjects (91.7%) presented with muscular disease remission, compared to 55.6% of non-IVIG-treated subjects ( $p = 0.007$ ). During long-term IVIG treatment (up to 48 months), 16.7% of subjects presented with muscular relapses, which is significantly less than those who received no or only a few IVIG courses. The overall relapse-free period from any DM symptom was  $38.5 \pm 24.3$  months [Kampylafka, 2012].

SCIG has also been shown to be efficacious in treating subjects with DM/PM in smaller uncontrolled studies [Schleinitz et al, 2008; Danieli et al, 2011; Danieli et al, 2014; Gelardi et al, 2014; Cherin et al, 2016]. Long-term use of SCIG therapy has been described by Cherin [Cherin et al, 2016]. In doses of 1.9 g/kg monthly, 19 subjects were treated for a mean of 18.8 months. Median doses infused were 180 mL/week using 2 infusion pumps; similar to the infusion parameters in this study. Although these smaller studies have shown promising results, no large-scale or randomized controlled studies are available to corroborate the efficacy of SCIG against placebo in subjects with DM, which is a reason for the initiation of this study.

This study will build on previous evidence that has shown efficacy in the first 3 to 6 months of IgG treatment and will investigate whether the initial improvement can be sustained for 6 months to up to 7 years.

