#### **4.3.2.1 Procedures for Handling Withdrawals**

If a subject is withdrawn from the study during Study Period 1 or Study Period 2, attempts will be made to complete and document the Week 53 assessments. If the subject is withdrawn from the study after receiving IMP, every effort will be made to ensure that the relevant safety assessments, including the 4-week Safety Follow-up Telephone Call (only in Study Period 1 and Study Period 2), are completed.

If the subject is withdrawn from the study during Study Period 3, the EOP3 Visit assessments must be performed. The subject may also be asked by the investigator to complete additional study assessments. If, during Study Period 3, the investigator determines that the subject is no longer benefiting from IgPro20 and/or is showing signs of clinical deterioration in the status of DM, the subject must be discontinued from the study. If the subject withdraws from the study, and also withdraws consent for disclosure of future information, CSLB may retain and continue to use any data and samples collected before withdrawal of consent.

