## 10.4.5 Interim Analysis

No interim analysis for sample size re-estimation, futility stopping, or efficacy stopping is planned.

The primary data analysis (EOP1 analysis) will be done after all subjects have completed all assessments for Study Period 1. At the time of the EOP1 analysis additional AE, efficacy, and pharmacokinetic data of Study Period 2 will be analyzed. Efficacy analysis of the Study Period 2 data will be restricted to all subjects completing or discontinuing prematurely Study Period 2 at the time of data cut-off for the EOP1 analysis; the adverse events analysis will include all subjects treated in any study period at the time of data cut-off for EOP1 analysis; the pharmacokinetic analysis will include all subjects who have completed the Rich PK sampling at Week 37.

Two additional analyses will be done after all subjects have completed all assessments for Study Period 2 (EOP2 analysis) and one after all subjects have completed all assessments for Study Period 3.

## 10.5 Statistical Analyses and Methods for Study Period 3

All analyses for Study Period 3 will be based on the SAF-P3.

All secondary efficacy endpoints and all exploratory endpoints referring to Study Period 3 will be analyzed descriptively. TEAEs occurring during Study Period 3 will be summarized descriptively including frequency counts and percentages of subjects and the number of events and TEAE rate per time at risk in analogy to [Section 10.4.3](#).

A complete description of the statistical analyses and methods will be available in the SAP.

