**Table 9: Periods and Reference Visits for Study Period 3**

Period	Start of period	Reference visit of period	End of period a
Week 53 – EOP3	Start date and time of the first IMP infusion at Week 53	Week 53 (before infusion of IMP)	EOP3

a The end of the period is the listed visit or the last visit before / at withdrawal.

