**Table 12: Exploratory Endpoints – Variables (Study Period 1 and Study Period 2)**

Endpoint	Variable	Type of summary measure
EQ-5D-5L	
 
• Pain/ discomfort
 
• Anxiety/ depression
 
	
 
• cumulative distribution function
 

	
 
• Utility index
 
• Health VAS
 
	
 
• continuous
 

WPAI-GH	
 
• Percent work time missed due to health
 
• Percent impairment while working due to health
 
• Percent overall work impairment due to health
 
• Percent activity impairment due to health
 
	
 
• continuous
 

TSQM-9	
 
• Effectiveness
 
• Convenience
 
• Global Satisfaction
 
• Item 1 to Item 9
 
 
Change from Baseline will not be summarized as there is no Baseline assessment for TSQM-9.
	
 
• continuous
 

Endpoint	Variable	Type of summary measure
Timed Up and Go	• Timed Up and Go	• categorical (see Section 8.2.29)
5-D Itch score	• Total score	• continuous
Muscle enzymes	Serum levels of • CK (IU/L) • LDH (IU/L) • AST (IU/L) • ALT (IU/L) • aldolase (IU/L)	• continuous
Serum IgG	• IgG serum concentrations	• continuous
	• IgG PK parameters $C_{max}$ , $C_{trough}$ , and AUC	• see Section 12
IIM autoimmune antibody panel	• MSA • MAA • ANA	• Response, categorical, continuous
HAQ	• Pain VAS	• continuous
MDAAT	• VAS Constitutional Disease Activity • VAS Cutaneous Disease Activity • VAS Skeletal Disease Activity • VAS Gastrointestinal Disease Activity • VAS Pulmonary Disease Activity • VAS Cardiovascular Disease Activity • VAS Other Disease Activity	• continuous
CDASI	• Total score • Total damage score	• continuous
Reduction of oral concomitant corticosteroid treatment	• Percent reduction of average daily dose	• continuous

The exploratory endpoints listed in Table 13 for Study Period 3 will be summarized descriptively only as described in Section 10.5. The data will be presented by sequence and overall including

visits from all 3 study periods based on the SAF-P3. Reference visits are described in Section 8.2.1.

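### Scheduled-visit efficacy summaries in Study Period 3 are conditional on not having been removed for loss of benefit, and no planned analysis gives the time to, or the share of entrants with, such loss.

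*Protocol*

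**What the plan says.** **Purpose.** Protocol 3.3.1 says the study "will investigate whether the initial improvement can be sustained for 6 months to up to 7 years". Protocol 2.3.1 lists efficacy after Week 53 as an exploratory objective; the secondary objective for that time (2.2.1) is safety only.

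**Entry and exit.** Entry needs TIS of at least 20 at Week 49 (protocol 4.1.3). After that, if the investigator judges that a subject "is no longer benefiting from IgPro20 and/or is showing signs of clinical deterioration in DM status, the subject must be discontinued from the study" (4.3.1, repeated in 4.3.2.1). There is no later follow-up: "Subjects who discontinue IMP during Study Period 3 will be withdrawn from the study". In Periods 1 and 2, by contrast, subjects who stop treatment are encouraged to stay for assessments.

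**Exit data.** "If the subject is withdrawn from the study during Study Period 3, the EOP3 Visit assessments must be performed" (4.3.2.1). The notes to the Period 3 schedule add that "all EOP3 assessments will be performed at the study visit where subjects discontinue/end study participation". The EOP3 visit includes four core set measures, CDASI and EQ-5D-5L (8.5.5.4). SAP Table 9 defines the close of the period: "The end of the period is the listed visit or the last visit before / at withdrawal".

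**Analysis.** Protocol 10.5: "All secondary efficacy endpoints and all exploratory endpoints referring to Study Period 3 will be analyzed descriptively". SAP 10.6: "The exploratory endpoints listed in Table 13 for Study Period 3 will be summarized descriptively only as described in Section 10.5". SAP 10.5 plans no imputation and, for continuous variables, adds a timepoint for each subject's last visit in the period. SAP Table 13 lists continuous summaries and EQ-5D-5L distribution functions. It contains no time-to-event variable and no proportion of entrants who keep their improvement. SAP 9.1 tabulates reasons for discontinuation by period.

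**The concern.** Losing benefit is both the outcome that a durability question asks about and the reason a subject leaves. A summary at a scheduled visit is therefore conditional on the investigator not yet having judged that benefit was lost. Such a mean can stay close to flat while a growing share of entrants has left for that reason, and the distortion favours IgPro20.

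What is at stake is the long-term description. A reader who takes the by-visit tables as evidence that improvement lasts would be reading a selected group, and the displays that do include leavers do not say how long benefit lasted.

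**Working it through.** The documents state no sample size, rate or target for Period 3 efficacy, so there is no plan figure to reproduce. The check has two parts.

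**1. Where a leaver's data go.**
- Data are reported by nominal visit (SAP 8.2.7). A subject removed for deterioration is measured at the exit visit, and that value is filed as EOP3, not under the scheduled week.
- It therefore enters the EOP3 summary and, for continuous variables, the last-individual-visit summary. Both mix subjects who left early for loss of benefit with subjects who reached the end of the study.
- The EQ-5D-5L domains in Table 13 are summarised as distribution functions, so the last-visit timepoint, specified for continuous variables, does not cover them.
- SAP 10.5 names only Weeks 1-25 and 25-53 as its periods. Its use in Period 3 rests on the cross-reference from SAP 10.6.
- The disposition table counts exits by reason but has no time axis and no link to efficacy.

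**2. Illustration of size, on assumed inputs.** Let h be the probability of losing benefit per 24-week interval, and let each loss be a 2 cm worsening on the Physician Global VAS from Week 53, followed by exit. Others stay unchanged. After k intervals:
- share still attending = (1 − h)^k
- mean worsening at the scheduled visit = 0, by construction, since every worsened value is filed as EOP3
- EOP3/last-visit mean = 2 × (1 − (1 − h)^k) cm

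| h per 24 weeks | k (weeks) | Still attending | Scheduled-visit mean | EOP3/last-visit mean |
|---|---|---|---|---|
| 5% | 4 (96) | 81.5% | 0.00 cm | 0.37 cm |
| 10% | 4 (96) | 65.6% | 0.00 cm | 0.69 cm |
| 20% | 4 (96) | 41.0% | 0.00 cm | 1.18 cm |
| 5% | 7 (168) | 69.8% | 0.00 cm | 0.60 cm |
| 10% | 7 (168) | 47.8% | 0.00 cm | 1.04 cm |
| 20% | 7 (168) | 21.0% | 0.00 cm | 1.58 cm |

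For example, h = 10% and k = 4 gives 0.9^4 = 0.656 and 2 × (1 − 0.656) = 0.69.

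A simulation with gradual change is less stark. Each subject drifts by a normal step per interval (SD 0.6 cm) and leaves on reaching 2 cm. At 168 weeks:

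| Mean drift per interval | Scheduled-visit mean | Last-visit mean | All entrants, had they stayed |
|---|---|---|---|
| 0.05 cm | −0.18 cm | 0.32 cm | 0.34 cm |
| 0.1 cm | 0.04 cm | 0.65 cm | 0.70 cm |
| 0.2 cm | 0.38 cm | 1.22 cm | 1.40 cm |

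The scheduled-visit mean understates worsening in every case. The last-visit mean recovers most of it but carries no information on timing.

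**The case against.** A reader might infer that Period 3 efficacy is summarised only from those still attending, so that sustained benefit is built into the whole result. The documents do not support that. Exit assessments are mandatory, the period closes at or before withdrawal, and the last-visit timepoint includes leavers at their exit value. Numbers of observations are reported, and discontinuations are tabulated by reason and period, so attrition is visible.

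Further points also have weight. The exit rule is a judgement without a numeric threshold, and protocol 5.3.1 permits additional oral corticosteroid in Period 3 once continuing benefit has been verified, so some subjects may worsen and remain. Scheduled means need not be flat. Period 3 efficacy is exploratory, no hypothesis is tested, and 7 years is a maximum. The early part of the durability question falls in Period 2, where this exit rule does not apply. The rates used above are assumptions.

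All of this stands, and it limits the point to the scheduled-visit tables and to what is absent beside them. It does not supply the missing analysis: neither the last-visit summary nor the disposition counts show when benefit was lost or what proportion of entrants had kept it at a given time.

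**Conclusion.** The concern holds in this limited form. Scheduled-visit Period 3 summaries are selected on the outcome, in favour of IgPro20, and cannot by themselves answer the durability question in protocol 3.3.1. The EOP3 and last-visit summaries offset this in part, without a time axis.

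The size is unknown because no rate of loss is given. On the two-state assumptions, the gap between last-visit and scheduled-visit means is 0.37 to 1.18 cm at 96 weeks and 0.60 to 1.58 cm at 168 weeks. It rests on the assumed 5% to 20% loss per 24 weeks, the assumed 2 cm worsening at exit, and exit values being filed as EOP3.

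Only exploratory, descriptive analyses are affected. The primary and key secondary tests, and the power calculation behind the sample size, are untouched. The clinical exit rule itself is not questioned.

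**What to change.** In SAP 10.6 and Table 13, and in protocol 10.5:

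- **(a) Time to loss of benefit.** Add a display from Week 53 to discontinuation for lack of benefit or clinical deterioration, using the recorded reason and date, censored at administrative study end. Show exits for other reasons, such as adverse events or withdrawn consent, as competing events (a cumulative incidence curve).
- **(b) Proportion maintained.** At each 24-week visit, report the share of all SAF-P3 subjects due for that visit who remain on IgPro20 with maintained improvement. Count exits for lack of benefit or deterioration as not maintained, and state how other exits are counted.
- **Definition for (b).** Use a measure collected in Period 3, for example the protocol's own criterion of at least 2 cm improvement from Baseline on the Physician Global VAS. Show the Week 53 proportion as the starting value, since entry is decided on TIS. A TIS from the four measures collected is unsuitable. Missing measures score 0, so its maximum is 20 + 10 + 32.5 + 10 = 72.5 rather than 100, which is not comparable with Week 49.
- **Labelling.** Title the by-visit tables as subjects still on treatment. Place the number remaining, the exit reasons and the EOP3/last-visit summary beside them, and state explicitly that the last-visit timepoint applies to Period 3.

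The cost is SAP and protocol wording and a few extra outputs. The reason and date of discontinuation are already recorded under protocol 4.3.1, and no visit changes. The sponsor may have to report a less favourable durability figure.

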### **4.3.2 Subject Withdrawal from Study**

Subjects may withdraw from the study at any time at their own request or at the discretion of the investigator or CSLB. The investigator should record in the eCRF and in the subject's medical records the reason for study withdrawal, if provided by the subject in the case of withdrawn consent, and date of subject withdrawal.

In accordance with the International Council for Harmonisation of Technical Requirements for Pharmaceuticals for Human Use (ICH) principles of Good Clinical Practice (GCP), the investigator always has the option to advise a subject to withdraw from treatment or the study if the subject's safety or well-being is compromised by his or her further participation in the study. Concern for the interests of the subject must always prevail over the interests of the study.

#### **4.3.2.1 Procedures for Handling Withdrawals**

If a subject is withdrawn from the study during Study Period 1 or Study Period 2, attempts will be made to complete and document the Week 53 assessments. If the subject is withdrawn from the study after receiving IMP, every effort will be made to ensure that the relevant safety assessments, including the 4-week Safety Follow-up Telephone Call (only in Study Period 1 and Study Period 2), are completed.

If the subject is withdrawn from the study during Study Period 3, the EOP3 Visit assessments must be performed. The subject may also be asked by the investigator to complete additional study assessments. If, during Study Period 3, the investigator determines that the subject is no longer benefiting from IgPro20 and/or is showing signs of clinical deterioration in the status of DM, the subject must be discontinued from the study. If the subject withdraws from the study, and also withdraws consent for disclosure of future information, CSLB may retain and continue to use any data and samples collected before withdrawal of consent.

#### **4.3.3 Subjects Lost to Follow-up**

If a subject repeatedly fails to return for scheduled visits, the site must attempt to contact the subject and counsel the subject on the importance of maintaining the assigned study visit schedule and ascertain whether or not the subject wishes to and/or should continue in the study. All attempts to contact the subject should be documented in the subject's medical record.

A subject will be considered lost to follow-up if he or she repeatedly fails to return for scheduled visits and is unable to be contacted by the study site. Subjects lost to follow-up will be considered to have withdrawn from the study.

#### **4.3.4 Replacement Policy**

Subjects withdrawn from the study will not be replaced.

#### **4.3.5 Consequences of Subject Withdrawal or IMP Discontinuation**

Subjects who have been withdrawn from the study or who have discontinued IMP before Week 25 will be considered non-responders for the primary endpoint analysis, except if withdrawal or discontinuation was due to the Ukraine war (see [Section 10.4.2](#)) Withdrawal from IMP during Study Period 1 or Study Period 2 renders a subject ineligible for participation in Study Period 3 of this study.

## 5 Study Interventions

### 5.1 Investigational Products

#### 5.1.1 Description of IgPro20

Substance name	IgPro20
Active substance	Human normal IgG
Trade name	Hizentra®
Storage	Temperature-controlled and monitored conditions at 2 to 8°C in a secure storage area at the site
Dosage form	Liquid, ready-to-use 20% IgG solution stabilized with 250 mmol/L L-proline and 20 mg/L polysorbate 80

IgG = immunoglobulin G.

IgPro20 for SC administration will be provided as a 20% IgG solution in a vial containing 10 g IgG in a 50 mL volume. IgPro20 will be manufactured by CSLB, in accordance with ICH GMP guidelines and local regulatory requirements.

Information on the preparation and SC administration of IgPro20 is provided in the IMP manual.

#### 5.1.2 Description of Placebo

Substance number	Not applicable
Substance	Placebo
Trade name	Not applicable
Storage	Temperature-controlled and monitored conditions 2 to 8°C in a secure storage area at the site
Dosage form	2% human albumin solution in 250 mmol/L L-proline and 20 mg/L polysorbate 80 manufactured from the licensed, pasteurized CSLB human albumin 5% final product

CSLB = CSL Behring.

Placebo for SC administration will be manufactured by CSLB, and provided in vials of 50 mL volume.

